9.6.3.2. Guidelines for Prolonged QTcF Interval

Recommended dose interruption and management of treatment-related prolonged QTcF interval is provided in Table 10.

Table 10:Recommended Dose Interruption and Management of Treatment-related
Prolonged QTcF Interval

Toxicity Grade CTCAE v5.0 (ECG QTc interval prolonged)	Dose Interruption and Management
Grade 2 (QTc 481-500 ms)	Continue study drugContinue ECG monitoring per protocol
Grade 3 (QTc ≥501 ms; >60 ms change from baseline)	 Hold treatment with study drug Continue close ECG monitoring and consult cardiologist Upon resolution to Grade 1 or baseline in ≤14 days, may resume study treatment at same dose. If >14 days for resolution to Grade 1 or baseline, may resume study treatment at reduced dose.
Grade 4	 Discontinue study drug Continue close ECG monitoring and consult cardiologist

Abbreviations: CTCAE=Common Terminology Criteria for Adverse Events; ECG=electrocardiogram; QTc=QT interval corrected; QTcF=QT interval corrected by Fridericia's formula.

9.6.3.3. Guidelines for Dermatologic Adverse Events

Recommended dose interruption and management of treatment-related skin and subcutaneous disorder and recommendations for management of dry skin are presented in Table 11.

General guidelines for treatment-related dermatologic adverse events:

- Symptoms and signs of hypersensitivity reaction should be monitored at each clinic visit. Refer to Section 9.6.1 for dose interruption guidance
- Use "Rule of 9s" (refer to Appendix 2) to calculate body surface area (BSA) for CTCAE grading

- Participant should be advised to use fragrance-free detergents and soaps, wear sunscreen with sun protection factor ≥30, and moisturize the skin at least once daily, preferably twice daily
- Standardized photos for any Grade ≥2 dermatologic AEs should be submitted to the Sponsor
- A skin biopsy sample (ie, punch biopsy) may be collected locally if a participant experiences a treatment-related dermatologic AE. If collected, the sample will be shipped to a central laboratory and may be analyzed for histopathology and potentially for molecular markers. Specific instructions on collection and shipping of samples will be provided in a separate laboratory manual

Toxicity Grade (CTCAE v5.0)	Maculopapular Rash	Pruritus/Urticaria	Eczema	Dry Skin ^a
Grade 1	 Continue treatment with study drug Treat with mid- to high-potency topical corticosteroid bid 	 Continue treatment with study drug Treat with cooling lotions containing menthol and/or camphor Treat with mid- to high-potency topical corticosteroid bid 	 Continue treatment with study drug Treat with mid- to high-potency topical corticosteroid bid 	 Continue treatment with study drug Apply moisturizing creams/lotions without fragrances/irritants (eg, Oncoderm Body Rx spray; Eucerin original)
Grade 2	 Continue treatment with study drug Treat with high-potency topical corticosteroid 1-2 times per day Treat with anti-H1 therapy (if rash is associated with symptoms such as pruritus and/or urticaria) or GABA agonists Standardized photographs^b Dermatologic consultation recommended 	 Continue treatment with study drug Treat with high-potency topical corticosteroid bid Initiate anti-H1 therapy or GABA agonists Standardized photographs^b Dermatologic consultation recommended 	 Continue treatment with study drug Treat with high-potency topical corticosteroid bid Treat with anti-H1 therapy or GABA agonists (if eczema associated with pruritis) Standardized photographs^b Dermatologic consultation recommended 	 Continue treatment with study drug Apply moisturizing creams/lotions without fragrances/irritants (eg, Oncoderm Body Rx spray; Eucerin original)
Grade 3	 Hold treatment with study drug Check CBC/differential-evaluate for eosinophilia Standardized photographs^b 	 Hold treatment with study drug Standardized photographs^b Refer for dermatologic consultation and obtain skin biopsy 	 Hold treatment with study drug Standardized photographs^b 	 Hold treatment with study drug Use mid-potency topical steroid (eg, triamcinolone acetonide 0.1%) bid

Table 11: Recommended Dose Interruption and Management of Treatment-related Dermatologic Adverse Events

Toxicity Grade (CTCAE v5.0)	Maculopapular Rash	Pruritus/Urticaria	Eczema	Dry Skin ^a
	• Refer for dermatologic consultation and obtain skin biopsy	 Consider anti-IgE antibody following dermatologic evaluation 	• Refer for dermatologic consultation and obtain skin biopsy	PLUS moisturizing creams/lotion without fragrances/irritants (eg,
	 Treat with oral corticosteroids following dermatologic evaluation (prednisone 0.5 mg/kg/day) for 10-14 days 	• Once AE resolves to Grade ≤1, restart study drug at 1 dose level reduction	 Treat with oral corticosteroids following dermatologic evaluation (prednisone 0.5 mg/kg/day) for 10-14 days 	Oncoderm Body Rx spray; Eucerin original) • Once AE resolves to Grade ≤1, restart study drug at 1 dose level reduction
	• Once AE resolves to Grade ≤1, may resume study drug at 1 dose level reduction		• Consider interleukin-4 receptor alpha antagonist following dermatologic evaluation	
			• Once AE resolves to Grade ≤1, restart study drug at 1 dose level reduction	

Abbreviations: AE=adverse event; bid=twice daily; CBC=complete blood count; CTCAE=Common Terminology Criteria for Adverse Events; GABA=gamma-aminobutyric acid; H1=histamine-1; IgE=immunoglobulin E.

^a Source: Lacouture et al, 2021

^b Guidance for standardized photographs will be provided separately

9.7. Study Drug Compliance

To ensure study drug compliance, the Investigator or designee must supervise all study drug dosing that occurs at the site. At each visit, site personnel must review that the participant is compliant with study drug dosing by reviewing the dosing diary and remind the participant of study drug dosing requirements. Compliance must also be assessed by ongoing study drug count.

If a participant demonstrates continued noncompliance of study drug dosing despite educational efforts, the Investigator must contact the Sponsor to discuss discontinuation of the participant from the study.

9.8. Study Drug Accountability

The study center is required to maintain drug accountability records that indicate the study drug's delivery date to the site, inventory of study drug at the site, study drug dispensed to each participant, and study drug returned to the Sponsor or destroyed at site. Accountability records must include dates, quantities, lot numbers, and participant numbers. Sponsor or its designee will review drug accountability records at the site during monitoring visits.

9.9. Study Drug Handling and Disposal

Participants must be instructed to bring all empty, partially used, and full study drug bottles to each clinic visit. The site staff or pharmacy personnel (as appropriate) must retain all materials until returned to the Sponsor or its designee, or sent for destruction according to the site's standard procedure.

9.10. Concomitant Medications and Therapies

All intercurrent medical conditions should be treated by the Investigator according to current community standards of care. Participants may also receive medications for symptomatic relief (eg, analgesics, laxatives, anti-emetics).

9.10.1. Permitted Medications and Therapies but Used with Caution

The following medications should be taken with caution:

• Medications that **may possibly** prolong the QT interval (see Appendix 1)

9.10.2. Prohibited Medications and Therapies

The following medications, substances, and procedures are prohibited during study treatment:

- Initiation of any other anti-tumor therapy for TGCT, including radiation or surgery
- Investigational therapy or investigational procedures of any kind

- The use of intra-articular steroid injections for treatment of TGCT; use of intra-articular steroids for non-TGCT condition is permitted
- Acetaminophen usage exceeding 3 g/day
- Proton-pump inhibitors: discontinue at least 4 days prior to the first dose of study drug
- Medications that are BCRP or OCT2 substrates: discontinue at least 4 days or 5×halflife (whichever is longer) prior to the first dose of study drug
- Medications with a **known risk** of prolonging the QT interval: discontinue at least 14 days or 5×half-life (whichever is longer) prior to the first dose of study drug (see Appendix 1)
- Prophylactic use of myeloid growth factors (eg, G-CSF, GM-CSF)

10. DISCONTINUATION OF STUDY TREATMENT AND PARTICIPANT DISCONTINUATION

10.1. End-of-Treatment

A participant is free to withdraw from the study drug treatment for any reason and at any time without giving reason for doing so and without penalty or prejudice. The Investigator is also free to terminate a participant's study drug treatment at any time if the participant's clinical condition warrants it. The primary reason for treatment discontinuation must be determined using the following categories:

- Protocol Violation
- Progressive Disease by IRR
- Progressive Disease by Investigator Assessment
- Noncompliance with Study Drug
- Adverse Event
- Death
- Withdrawal by Participant (Treatment Discontinuation)
- Physician's Decision
- Pregnancy
- Lost to Follow-up
- Study Terminated by Sponsor
- Other (Any other reason that in the opinion of the Investigator, would justify removing the participant from the study drug, based on the best interest of the participant)

Refer to schedule of assessments for data to be collected at the time of treatment discontinuation, follow-up, and for any further evaluations that need to be completed. Additional information relating to treatment discontinuation due to disease progression is provided in Section 10.5.

10.2. End of Study

A participant is considered to have completed the study if s/he has completed Part 1, Part 2, and all Follow-up visits (Safety Follow-up and Disease Follow-up) of the study.

The primary reason for discontinuation or withdrawal of a participant from the study must be determined using the following categories:

- Completed
- Completed (After Early Treatment Discontinuation)
- Progressive Disease by IRR
- Progressive Disease by Investigator Assessment

- Subsequent TGCT Therapy and/or Surgery
- Death
- Withdrawal by Participant (Withdrawal of Consent)
- Lost to Follow-up
- Physician's Decision
- Study Terminated by Sponsor
- Other (Any other reason that in the opinion of the Investigator, would justify removing the participant from the study, based on the best interest of the participant)

If a participant voluntarily withdraws from the study, the Investigator should attempt to contact the participant to determine the reason(s) for withdrawal. No additional study procedures will be performed and no study-related information will be collected after the participant withdraws consent for this study.

10.3. Replacement of Participants

Participants will not be replaced in this study.

10.4. Lost to Follow-up

A participant will be considered lost to follow-up if both of the following occur:

- Participant misses 2 consecutive study visits and is subsequently unable to be contacted by phone call (3 documented attempts by phone within 2 weeks following the second missed visit)
- Participant does not respond within 2 weeks to a registered letter sent after the 3 attempted phone contacts

10.5. Disease Progression

Part 1 Double-blind

Participants randomized to placebo in Part 1

Participants randomized to placebo with confirmed disease progression by IRR in Part 1 are eligible for crossover to receive open-label vimseltinib in Part 2. Once disease progression is confirmed by IRR, the participant will be unblinded and will follow End of Part 1 assessments outlined in Table 1. After unblinding, the participant may start the crossover procedures on Cycle 1 Day 1 crossover. If the participant declines to continue to Part 2, then the participant will discontinue, complete EOT assessments, and Safety Follow-up Visit as described in Table 1. Disease Follow-up is not required.

Participants randomized to vimseltinib in Part 1

Participants randomized to vimseltinib with confirmed disease progression by IRR in Part 1 will discontinue treatment, complete EOT assessments, and Safety Follow-up Visit as described in Table 1. Disease Follow-up is not required.

Part 2 Open Label

Participants with disease progression will discontinue treatment and complete EOT assessments and Safety Follow-up as described in Table 2 and Table 3. Disease progression must be confirmed by IRR until Week 96 (ie, 2 years after first dose of study drug). Disease Follow-up is not required.

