11.5.1. End of Part 1 Visit

The End of Part 1 visit and the first Part 2 visit both occur at Week 25. The End of Part 1 visit serves as both the last visit of Part 1 and entry into Part 2. The following assessments for the End of Part 1 visit must be performed before unblinding: MRI, ROM, AE Review, Investigator questionnaires, and PRO questionnaires as noted below in Table 12. All End of Part 1 assessments must be completed before dosing in Part 2. After unblinding, the assessments to be completed at the first Part 2 visit are shown in Table 13.

Participants who are unblinded in Part 1 due to confirmed disease progression by IRR and were on placebo will cross over to Part 2, and will need to complete End of Part 1 Assessments per

Table 1. The MRI, ROM assessment, and PRO questionnaires will not need to be repeated if completed within 30 days of End of Part 1 Visit.

Table 12:End of	of Part 1	Visit
-----------------	-----------	-------

End of Part 1 / Week 25		
Assessments	Timing	
 MRI of affected joint^a ROM assessment^b 	 May utilize -7d window and must perform while blinded 	
 AE review Completion of Investigator questionnaires (CGIC/CGIS) PRO questionnaires 	• At End of Part 1 visit and must perform while blinded	
 Review concomitant medications/procedures Full physical exam Vital signs and weight Pregnancy test^c Collection of central safety labs^d Urinalysis 12-lead ECG 	• Must be completed before dosing in Part 2, may be performed while blinded or after unblinding	

Abbreviations: AE=adverse event; CGIC=clinician global impression of change; CGIS=clinician global impression of severity; d=day; ECG=electrocardiogram; MRI=magnetic resonance imaging; PRO=patient-reported outcome; ROM=range of motion.

^a Confirmation that MRI has been performed satisfies unblinding criteria.

^b ROM assessment (active and passive) of both the affected joint and non-affected joint will be performed at the End of Part 1 visit.

^c Pregnancy testing must be done within 3 days of dosing in Part 2.

^d Safety labs to be completed within 3 days of dosing in Part 2

Note: All of the above procedures must be completed as outlined above before dosing in Part 2.

Table 13:First Part 2 Visit

Week 25 Cycle 1 Day 1 Crossover For participants crossing over from placebo		Week 25 Cycle 7 Day 1 For participants who were assigned vimselting in Part 1	

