11.9.13.2. Range of Motion Assessment

The ROM of the affected and contralateral non-affected joint will be assessed using goniometry according to the relevant schedule of assessments. The modality of assessment will be active, ie, measuring a motion produced by the participant's voluntary, unassisted muscle contraction, and passive, ie, measuring a motion produced by the application of external force by an examiner. Active and passive assessments of the affected joint will be performed at screening and thereafter according to the relevant schedule of assessments. Active and passive assessments of the non-affected contralateral joint will only be performed at screening and End of Part 1 visit.

The joint, side of body, motions assessed, and degrees measured (the start and end position of motion) will be recorded for active and passive motion. Results should be documented on the ROM form provided by the Sponsor. Adequately trained site personnel (physiotherapist or orthopedic surgeon) who are blinded to study treatment should perform the ROM assessment. Every effort should be made to have the same assessor conduct all ROM assessments for each participant throughout the protocol. All motions applicable to a specific joint should be collected for the duration of the clinical study.

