8.1. Baseline

For all evaluations unless otherwise noted, baseline is defined as the most recent non-missing measurement prior to the first administration of study drug.

For the PROs collected multiple times during the screening period such as the Brief Pain Inventory (BPI) Numeric Rating Scale (NRS) for worst pain and average pain, and the NRS for worst stiffness, baseline will be the average of measurements taken during the period prior to Cycle 1 Day 1 which are the 14 days of assessments closest to and prior to Cycle 1 Day 1. A

participant must have at least 4 assessments available to compute this average, otherwise it is set to missing. For crossover participants and data from Part 2, baseline is defined to most recent measurement prior to first administration of vimseltinib. For BPI and NRS, the crossover baseline is defined as the average of Weeks 2 and 3 of Cycle 6 in Part 1.

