8.3. Analysis Visit Window

For by-visit (or cycle) statistical summaries, data will be analyzed according to the scheduled visit assigned on the eCRF (also referred to as the nominal visit). Otherwise, data collected as unscheduled assessments will be mapped to a scheduled visit using a visit window from Cycle 1 Day 1. The visit window for a specific visit of interest will go from the midpoint between the preceding visit and the visit of interest to the midpoint between the visit of interest and the subsequent scheduled visit.

For PRO, cycles will be mapped based on the expected length of 28 days to determine where assessments will be assigned based on the participant's Day 1 of each cycle.

If there are more than one unscheduled result, visit date will be used to calculate study day and the valid assessment within the visit window closest to the target study day will be used. If two or more assessments are the same distance apart from the target study day, then the earliest assessment will be used. The early termination visit may also be mapped to a derived visit window. Data that are collected from unscheduled visits and cannot be mapped to a scheduled visit will not be included in the by-visit summary tables but will be presented in the listings.

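### Protocol 10.5 unblinds placebo early progressors before End of Part 1 assessments that 11.5.1 wants done blinded, and the SAP's visit rule can time their active ROM differently by arm

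*Protocol*

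**What the plan says.** **Order of unblinding.** Protocol 10.5, on placebo participants: "Once disease progression is confirmed by IRR, the participant will be unblinded and will follow End of Part 1 assessments outlined in Table 1". Protocol 11.5.1: "The following assessments for the End of Part 1 visit must be performed before unblinding: MRI, ROM, AE Review, Investigator questionnaires, and PRO questionnaires". The next paragraph of 11.5.1 nevertheless describes participants already unblinded for progression as still having the End of Part 1 assessments to complete.

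**The other arm.** Protocol 10.5: "Participants randomized to vimseltinib with confirmed disease progression by IRR in Part 1 will discontinue treatment, complete EOT assessments". In Table 1 the EOT visit includes ROM (unless done in the previous 30 days), investigator questionnaires and patient questionnaires. Protocol 9.4.2 unblinds progressors in both arms.

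**Safeguards.** Protocol 11.5.1: "The MRI, ROM assessment, and PRO questionnaires will not need to be repeated if completed within 30 days of End of Part 1 Visit". Protocol 11.9.13.2 says that trained site staff "who are blinded to study treatment should perform the ROM assessment".

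**Visit assignment.** SAP 8.3: "data will be analyzed according to the scheduled visit assigned on the eCRF". Table 1 labels the End of Part 1 column Week 25. SAP 8.3 permits, but does not require, mapping an early termination visit to a window, and it maps PROs by 28-day cycle instead. SAP 9.10.2 windows End of Part 1 scans. SAP 9.10.3.2, on ROM, has no matching sentence.

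**Crossover baseline.** SAP 8.1, for BPI and NRS: "the crossover baseline is defined as the average of Weeks 2 and 3 of Cycle 6 in Part 1".

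**The concern.** Active ROM is the first functional endpoint in the hierarchy, and everything below it is tested formally only if it succeeds. It depends on the participant's voluntary effort and on an examiner's reading, so knowledge of treatment matters. Under 10.5 a placebo progressor's ROM can be measured after the participant, investigator and site staff know the assignment.

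The visit also depends on the arm: End of Part 1 for placebo, EOT for vimseltinib. Under a nominal-visit rule the first can enter the model as Week 25 whenever it took place. The second enters only if someone chooses to map it; otherwise it is missing and is handled by the mixed model under missing at random. Comparable participants could then be represented differently in the two arms. Because 10.5 selects the visit by arm, the site must know the arm before it knows which visit to run.

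The baseline gap is a separate matter. It concerns the on-vimseltinib summaries of crossover participants, not the randomized comparison.

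**Working it through.** **1. The plan's own figure.** The documents give no count of early progressors and no SD for ROM, so there is no stated figure on this point to reproduce. The only power figure, 98% for ORR (35% vs 5%, 80 vs 40, two-sided Fisher exact), reproduces at 98.3% and does not depend on this issue.

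**2. Which hierarchy endpoints can the visit label affect?**
- *RECIST and TVS ORR:* no. Progression at Week 13, or at an unscheduled scan before Week 25, is non-response in both arms (SAP 9.10.2, Table 2; SAP 9.10.3.1).
- *Worst Stiffness and BPI-30:* no. The Week 25 value is the mean over Weeks 2 and 3 of Cycle 6, so an early visit-day entry is not used. Missing BPI-30 is non-response in both arms.
- *PROMIS-PF and EQ-VAS:* not moved to Week 25 by label, because PROs are cycle-mapped. An answer given after unblinding could still enter at its own cycle.
- *Active ROM:* yes. The model uses Weeks 13 and 25 and has no ROM-specific assignment rule.

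**3. When would a new ROM be taken, and where would it fall?** Week 13 is Day 85 and Week 25 is Day 169. Cycle 4 Day 1 ROM has a ±7-day window, Days 78 to 92. Adding 30 days, the no-repeat rule covers an End of Part 1 visit up to Day 108 to 122 (Day 115 if ROM was done on Day 85). On the ROM schedule the Week 25 window opens at (85 + 169)/2 = Day 127, the start of Week 19. If the preceding visit is instead read as Week 21 (Day 141), it opens at (141 + 169)/2 = Day 155.

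With Cycle 4 ROM on Day 85, a new early ROM labelled Week 25 would fall outside the day window on Days 116 to 126, or Days 116 to 154 on the second reading. Before that no new ROM is needed, but the SAP does not say whether the reused Week 13 value also counts as Week 25.

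**4. Illustrative size for ROM.** Assumptions: k of 40 placebo participants progress early; their recorded Week 25 value is off by s SD; normal approximation; no gain from repeated measures.

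- Bias = (k/40) × s
- SE = √(1/80 + 1/40) = 0.194 SD
- Type I error = Φ(bias/SE − 1.96) + Φ(−bias/SE − 1.96)

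Example, k = 2 and s = 0.5: bias = 0.025 SD; bias/SE = 0.129; type I error = 0.0336 + 0.0183 = 5.19%.

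| k of 40 | s = 0.25 | s = 0.5 | s = 1.0 |
|---|---|---|---|
| 1 | 0.006 SD; 5.01% | 0.0125 SD; 5.05% | 0.025 SD; 5.19% |
| 2 | 0.0125 SD; 5.05% | 0.025 SD; 5.19% | 0.05 SD; 5.77% |
| 4 | 0.025 SD; 5.19% | 0.05 SD; 5.77% | 0.10 SD; 8.11% |

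Losing 1 or 2 of 80 vimseltinib progressors whose values are 0.5 to 1.0 SD worse would add (1/80) × 0.5 = 0.006 to (2/80) × 1.0 = 0.025 SD.

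**5. Planned sensitivity analyses.** SAP 9.10.6 applies only if more than 10% of Week 25 data are missing. Its not-at-random analysis covers adverse-event discontinuations on vimseltinib, not progression.

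**The case against.** The strongest reply is that little is left once the safeguards are read. The only scheduled Part 1 MRI before Week 25 is at Cycle 4 Day 1, when ROM is also measured. A progression read promptly from that scan needs no new ROM, and the assessor should be blinded in any case. The before-unblinding rule in 11.5.1 can be read as governing the ordinary Week 25 visit, with progressors as an exception. No text says that an early End of Part 1 ROM carries the Week 25 label, and scans for that visit are explicitly windowed. The protocol describes the disease as slowly progressing.

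Much of this stands, and it limits the size. It does not close the gap. The 30-day rule omits the investigator questionnaires and AE review, and it does not help when progression is confirmed later from an unscheduled scan. A blinded assessor does not blind the participant whose active effort is being measured. If 11.5.1 intends an exception, it does not say that assessments may be done unblinded. The explicit windowing of scans makes the silence on ROM more noticeable.

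A reader might infer that questionnaires too are pulled to Week 25 by label, that vimseltinib progressors have no comparable visit, or that the plan favours vimseltinib. The documents do not support these. PROs are cycle-mapped. Vimseltinib progressors have an EOT visit with ROM and PROs. The direction is open: an early value has had less time to worsen, and expecting open-label drug could move effort or self-report either way. The calculation also treats the whole shift as bias, although a progressor's genuinely worse ROM is not bias; only the gap between recorded and true Week 25 values is.

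**Conclusion.** The concern holds in a limited form. The order in Protocol 10.5 conflicts with the blinding requirement in 11.5.1, and the conflict should be removed. For active ROM alone among the seven tested endpoints, the SAP leaves room for timing and missingness to differ by arm among early progressors.

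The effect is probably small. Type I error stays between 5.0% and 5.8% in every cell of the table except the most extreme (4 of 40 at 1.0 SD), where it reaches 8.1%. Those figures rest on assumed counts and shifts that the documents do not supply, and the sign could go either way. They show why the rule should be fixed in advance; they do not estimate a bias. The primary endpoint is untouched.

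The missing crossover baseline is certain for anyone who crosses over before Cycle 6, but it affects only on-vimseltinib summaries.

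**What to change.** - **Protocol 10.5 and 11.5.1:** reconcile them so that, once progression is confirmed, participants in both arms complete ROM, investigator questionnaires, PROs and AE review before anyone is unblinded. State how the 30-day no-repeat rule applies.
- **SAP 8.3:** assign early End of Part 1 and EOT ROM by the same study-day window in both arms, counting a value as Week 25 only if it lies inside that window. State whether the window is built on the ROM schedule or on all visits.
- **SAP 8.1:** for early crossovers, define the BPI and NRS baseline as Weeks 2 and 3 of the last completed cycle before first vimseltinib.
- **SAP 9.10.6:** add a ROM sensitivity analysis for early progressors in both arms, not conditional on the 10% missing-data trigger.

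The cost is minor protocol and SAP wording and one extra analysis, with no added visits.
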